9.1.3. Exploratory Efficacy Assessments

The primary (Section 9.1.1) and secondary efficacy measures (Section 9.1.2) will also be evaluated at 52 weeks as an exploratory efficacy assessment.

The following exploratory efficacy measures will be evaluated at 36 and 52 weeks (unless noted otherwise):

- proportion of patients achieving HbA1c target $\leq 6.5\%$ (48 mmol/mol)
- proportion of patients achieving $\geq 5\%$ body weight loss
- proportion of patients achieving $\geq 10\%$ body weight loss
- change in 6-point SMPG profile from baseline
- proportion of patients meeting the composite endpoint of HbA1c <7.0% (53 mmol/mol), no weight gain, and no documented symptomatic hypoglycemia
- proportion of patients meeting the composite endpoint of HbA1c <7.0% (53 mmol/mol), body weight loss $\geq 5\%$, and no documented symptomatic hypoglycemia or severe hypoglycemia
- changes in systolic blood pressure (SBP) and DBP from baseline
- changes from baseline in serum lipid parameters (total cholesterol, high density lipoproteins [HDL], low density lipoproteins [LDL], very low density lipoproteins [VLDL], and triglycerides)

- changes in insulin resistance as measured by the Homeostasis Model Assessment-2 (HOMA2) method (HOMA2-IR) (Caumo et al. 2006)
- β -cell function as measured by the HOMA2 method (HOMA2-%B), changes in fasting plasma glucagon, changes in fasting plasma glucagon adjusted for fasting glucose, changes in fasting insulin, and changes in C-peptide
- Diabetes Injection Device Experience Questionnaire (DID-EQ) scores at Week 12
- changes in EQ-5D-5L scores from baseline
- changes in Impact of Weight on Self-Perceptions Questionnaire (IW-SP) scores from baseline
- changes in Ability to Perform Physical Activities of Daily Living (APPADL) score from baseline

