10.3. Statistical Analyses

10.3.1. General Statistical Considerations

Statistical analysis of this study will be the responsibility of Eli Lilly and Company or its designee. Any change to the data analysis methods described in the protocol will require an amendment ONLY if it changes a principal feature of the protocol. Any other change to the data analysis methods described in the protocol, and the justification for making the change, will be described in the statistical analysis plan (SAP) or the clinical study report (CSR). Additional exploratory analyses of the data may be conducted as deemed appropriate.

Table GBGL.4 defines the populations to be used for analyses.

Efficacy and safety analyses will be conducted in the Intent to Treat (ITT) Population. There will be 2 primary estimands to compare treatment groups in terms of the primary measure of HbA1c change from baseline to Week 36.

One primary estimand will be an efficacy estimand (*de jure* effect) which will use the data collected before initiation of any rescue medication or premature treatment discontinuation to demonstrate the effect of treatment and avoid confounding effects of other antihyperglycemic agents (Little and Kang, 2014). The other primary estimand will be a treatment-regimen estimand (*de facto* effect) which will include data collected after initiation of other antihyperglycemic therapy and/or after premature treatment discontinuation.

The treatment-regimen (*de facto*) estimand is included as primary at the request of the US Food and Drug Administration (FDA). The efficacy (*de jure*) estimand will be considered primary for all other purposes, and will be applied to all efficacy outcomes unless otherwise specified to demonstrate effect of treatment and avoid confounding effects with other antihyperglycemic agents.

Both estimands will be tested at the full significance level of 0.05.

Analyses of safety parameters, except for hypoglycemia events, will be conducted in the ITT Population unless otherwise specified.

Unless otherwise noted, all tests of treatment effects will be conducted at a 2-sided alpha level of 0.05, and CIs will be calculated at 95%, 2-sided. All tests of interactions between treatment groups and other factors will be conducted at a 2-sided alpha level of 0.10.

The baseline will be at the randomization visit (Visit 3). If baseline data are missing, the last nonmissing measurement taken prior to Visit 3 will be used.

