10.3.3.4. Tertiary/Exploratory Efficacy Endpoints

The analysis of patients reaching HbA1c target $\leq 6.5\%$ and other binary outcomes will use the same model as that for HbA1c target <7.0% (53 mmol/mol) described in Section 10.3.3.2.

Longitudinal continuous variables will be analyzed using MMRM described in Section 10.3.1. The analysis will be conducted for on-treatment without rescue medication data. Log-normal-distributed data such as fasting glucagon may be analyzed using log scale.

Nonlongitudinal continuous variables such as 6-point SMPG, HOMA2-IR, and HOMA2-%B will be analyzed using LOCF by fitting a linear model with pooled country, treatment, baseline HbA1c strata as fixed effects, and corresponding baseline value as a covariate. Data transformation may be applied if data are not normally distributed.

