
Tertiary/Exploratory
 
To compare once weekly dulaglutide 4.5 mg and 3.0 mg to the 1.5 mg arm as measured by the primary and secondary outcome measures at 52 weeks.
 
To compare once weekly dulaglutide 4.5 mg and 3.0 mg to the 1.5 mg arm for exploratory measures through 36 and 52 weeks (unless noted otherwise).
	
 • The change in HbA1c from baseline • The change in body weight from baseline • Proportion of patients achieving HbA1c target <7.0% (53 mmol/mol) • The change in FSG from baseline • Proportion of patients achieving HbA1c target ≤6.5% (48 mmol/mol) • Change from baseline in 6-point self-monitored plasma glucose (SMPG) profile • Proportion of patients achieving ≥5% body weight loss • Proportion of patients achieving ≥10% body weight loss • Proportion of patients meeting the composite endpoint of HbA1c <7.0% (53 mmol/mol), no weight gain, and no documented symptomatic or severe hypoglycemia • Proportion of patients meeting the composite endpoint of HbA1c <7.0% (53 mmol/mol), body weight loss ≥5%, and no documented symptomatic or severe hypoglycemia • Changes from baseline in fasting plasma glucagon, HOMA2-%B, HOMA2-IR, and C-peptide • Changes from baseline in serum cystatin C and cystatin C-based assessment of eGFR • Incidence of initiation of rescue therapy for severe, persistent hyperglycemia • Changes from baseline in systolic blood pressure (SBP), diastolic blood pressure (DBP), and rate pressure product (RPP) • Changes from baseline in serum lipid parameters (total cholesterol, high density lipoproteins [HDL], low density lipoproteins [LDL], very low density lipoproteins [VLDL], and triglycerides) • Diabetes Injection Device Experience Questionnaire (DID-EQ) scores at Week 12 • Changes from baseline in EQ-5D-5L scores • Changes from baseline in Impact of Weight on Self-Perception Questionnaire (IW-SP) scores • Changes from baseline in Ability to Perform Physical Activities of Daily Living (APPADL) scores

Objectives and Endpoints

Abbreviations: eGFR = estimated glomerular filtration rate; EQ-5D-5L = European Quality of Life 5–Dimension 5 Level; HbA1c = glycated hemoglobin A1c; HOMA2-%B = β -cell function as measured by the Homeostasis Model Assessment-2 method; HOMA2-IR= insulin resistance as measured by the HOMA2 method; T2D = type 2 diabetes mellitus.

[figure not shown]
5. Study Design

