6.2. Patient Populations

Six patient populations are defined for the analyses in this study with detailed information listed in [Table GBGL.2](#). Unless otherwise specified, listings will include All Randomized Patients. Efficacy analyses will be conducted for the ITT Population, and safety analyses will be conducted for the Safety Population. The primary efficacy measure (change from baseline in HbA1c) will also be evaluated in the PP and Completers populations.

In all efficacy analyses, except for treatment-regimen estimands, all data after rescue and/or treatment discontinuation (Section 6.1) will be censored. Analyses of safety parameters will be conducted for the Safety Population including the postrescue therapy data unless otherwise specified.

Table GBGL.2. Populations for Analyses

Population	Description
Entered	All patients who sign informed consent
All Randomized	All patients who are randomized
Intent to Treat (ITT)	All patients who are randomized and take at least 1 dose of study medication for an assigned treatment arm ^a
Safety	All patients who are randomized and take at least 1 dose of study medication for the assigned treatment arm
Completers	All ITT patients who have an HbA1c measure at Week 36 (Visit 9), regardless of compliance with the protocol, rescue medication, or treatment discontinuation. However, data collected after rescue and/or treatment discontinuation will be excluded
Per Protocol (PP)	All ITT patients who meet all of the following criteria: 
 • Have no important protocol deviation that could impact the assessment of the primary endpoint (Section 6.8) • At least 75% compliant with study drug administration through Week 36 (Visit 9) • Complete the treatment period through 36 weeks (Visit 9) • Have a value of the primary efficacy measure (HbA1c) at Week 36 (Visit 9) excluding data collected after treatment discontinuation or initiation of new antihyperglycemic therapy

Abbreviation: HbA1c = glycated hemoglobin.

a Analyses using the treatment-regimen estimand will include all patients in the ITT population who have a baseline measurement for the parameter of interest, while analyses using the efficacy estimand will include patients in the ITT population who have a baseline and at least 1 postdose measurement for the parameter of interest.

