6.9.3. Planned Exploratory Analyses

Some of the planned exploratory analyses are described in Section 6.1. The remaining exploratory analyses are described in this section.

The analyses of proportions of patients reaching each target: HbA1c target $\leq 6.5\%$, body weight loss $\geq 5\%$, and body weight loss $\geq 10\%$ will employ the logistic regression model described in Section 6.1. The model for body weight target will be changed by replacing baseline HbA1c with baseline body weight as a covariate along with baseline HbA1c strata as a fixed effect. HbA1c target of the below 2 composite endpoints using LOCF will only apply a logistic regression model with an additional covariate of baseline body weight.

- HbA1c <7.0%, no body weight gain, and no documented symptomatic or severe hypoglycemia
- HbA1c <7.0%, body weight loss $\geq 5\%$, and no documented symptomatic or severe hypoglycemia

Longitudinal continuous variables (up to 52 weeks) such as HbA1c, body weight, FSG, and calcitonin will be analyzed using the MMRM described in Section 6.1. If the normality assumption is violated, an appropriate data transformation may be applied prior to analysis.

Nonlongitudinal continuous variables (up to 36 weeks) such as 6-point SMPG, C-peptide, fasting insulin, fasting glucagon, HOMA2-IR, and HOMA2-%B will be analyzed using LOCF by fitting a linear model with pooled country, treatment, and baseline HbA1c strata as fixed effects, and the corresponding baseline value as a covariate. A data transformation may be applied if data are not normally distributed.

The 6-point SMPG consists of measurements before and 2 hours after each of 3 meals within the same day. Each of the time points of the 6-point SMPG, mean of the premeal values, mean of the postmeal values, mean of all 6 time points, breakfast excursion, mid-day excursion, dinner excursion, and mean of all 3 excursions for each scheduled postrandomization visit will be summarized separately.

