6.10.4. Clinical Laboratory Evaluation

Analyses of eGFR, creatinine, and UACR are described in Section 6.10.1.2.9. For other laboratory safety parameters, summaries will be provided in this section. For continuous (numeric) laboratory analytes, including serum lipid parameters (total cholesterol, high-density lipoprotein cholesterol, low-density lipoprotein cholesterol, very-low density lipoprotein cholesterol, and triglycerides), the rank of the change from baseline to endpoint (Week 36 [Visit 9] for primary DBL, Week 52 [Visit 11] for final DBL) will be analyzed as detailed in Section 6.1. For qualitative laboratory analytes, the numbers and percentages of patients with normal and abnormal values will be summarized by treatment.

Each pancreatic enzyme (pancreatic amylase [p-amylase] and lipase) and the maximum postbaseline value will be summarized by treatment in a shift table using $>1 \times \text{ULN}$ and $\geq 3 \times \text{ULN}$ separately for the Safety Population, Safety Population with normal baseline value, and Safety Population with baseline value $>1 \times \text{ULN}$.

An MMRM with pooled country, baseline HbA1c strata, treatment, visit, and treatment-by-visit interaction as fixed effects will be fit to analyze each pancreatic enzyme up to Week 52 (Visit 11). In this model, the log-transformed (post first dose measure/baseline measure) will be

the response variable, and log-transformed baseline measure will be used instead of baseline measure. The variance-covariance structure selection is detailed in Section 6.1.

An ANCOVA model for Week 36 (Visit 9) measurement using LOCF will be fit with the same model as the aforementioned MMRM but removing all terms containing visit.

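### Serum lipids are listed as an exploratory efficacy measure, but the only SAP analysis naming them is an all-data rank test: no on-treatment-without-rescue analysis and no adjusted dose difference in lipid units is specified

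*SAP*

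**What the plan says.** Protocol 9.1.3 introduces its list with "The following exploratory efficacy measures will be evaluated at 36 and 52 weeks (unless noted otherwise", and the list includes "changes from baseline in serum lipid parameters (total cholesterol, high density lipoproteins [HDL" and the remaining lipid fractions. The SAP objectives table (Section 4) repeats the lipid endpoint under Tertiary/Exploratory.

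Protocol 10.3.1 says that the efficacy estimand "will be applied to all efficacy outcomes unless otherwise specified", and SAP 6.1 carries the same default. SAP 6.2 censors data after rescue or treatment discontinuation in every efficacy analysis other than the treatment-regimen ones. For safety it says: "Analyses of safety parameters will be conducted for the Safety Population including the postrescue therapy data unless otherwise specified".

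The SAP names a lipid analysis once, in 6.10.4 under Safety Analyses: "For continuous (numeric) laboratory analytes, including serum lipid parameters". That section takes the rank of the change from baseline to Week 36 (primary lock) or Week 52 (final lock) and refers to SAP 6.1 for the method. There, safety laboratory measures get an ANOVA on ranks of the LOCF change, with treatment as the fixed effect.

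Other continuous exploratory measures are handled in SAP 6.9.3: "Nonlongitudinal continuous variables (up to 36 weeks) such as 6-point SMPG, C-peptide, fasting insulin, fasting glucagon, HOMA2-IR, and HOMA2-%B will be analyzed using LOCF". The model there has pooled country, treatment and baseline HbA1c stratum as fixed effects and the variable's own baseline as covariate. Lipids are not named.

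**The concern.** A measure that the protocol classes as efficacy is analysed by the SAP only as a safety laboratory test, and the change brings a different data rule and a different scale.

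Patients who permanently stop study drug stay in the trial and should receive another glucose-lowering treatment; rescued patients also take one. Their later lipid values partly reflect that treatment or the absence of dulaglutide. A comparison that keeps those values is closer to a treatment-regimen effect than to the efficacy estimand that is the default for efficacy outcomes.

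A rank analysis gives a p-value but no dose difference that a reader can interpret in lipid units. With treatment as the only effect, it also makes no use of the baseline lipid value, the country or the HbA1c stratum. At stake is the usefulness of an exploratory result, not a confirmatory claim.

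**Working it through.** The point rests on setting the sections side by side. The arithmetic at the end is illustration only.

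1. **Class of the endpoint.** Protocol 9.1.3 makes lipids an exploratory efficacy measure at Weeks 36 and 52. They are not among the secondary safety endpoints in Protocol Section 4.

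2. **Default data rule for that class.** Efficacy estimand (Protocol 10.3.1, SAP 6.1), with censoring after rescue or drug discontinuation (SAP 6.2).

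3. **Data rule actually reached.** SAP 6.10.4 is a safety section, so SAP 6.2 keeps post-rescue data in so many words. Retention of off-drug values has to be inferred: SAP 6.1 runs the tables to Week 36 or Week 52 or to *study* discontinuation, and Protocol 8.1.1 keeps patients in the trial, with all measurements, after they stop drug.

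4. **Output.** SAP 6.1 provides mean, SD and median of actual values and of change, by visit and arm, for continuous measures, so changes in lipid units will be shown. It also promises LS mean differences with 95% CIs. The only lipid model is on ranks, however, so those would be on the rank scale.

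5. **Comparison with neighbours.** The Schedule of Activities draws fasting lipids, insulin, C-peptide and glucagon at the same visits: 3, 9, 11 and early termination.

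| | C-peptide, insulin, glucagon (SAP 6.9.3) | Lipids (SAP 6.10.4) |
|---|---|---|
| Data | censored under SAP 6.2 | post-rescue kept; off-drug kept by inference |
| Scale | measured units or a transformation | ranks |
| Adjustment | country, HbA1c stratum, own baseline | none |

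Blood pressure, also in Protocol 9.1.3, is analysed in the SAP's safety section, but by a repeated-measures model in its own units (SAP 6.10.3).

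6. **Illustration of dilution.** The plan expects 600 × 0.85 = 510 per arm to complete 36 weeks, which leaves 90. Assume that r of those 90 stay, are off drug and give a Week 36 sample, equally in each arm, and that their dose difference is wholly lost. The off-drug share is r/(510 + r).
   - r = 60: 60/570 = 10.5%.
   - r = 90: 90/600 = 15%.
   - With 30 to 60 rescued patients per arm as well (assumed), the affected share is (60 + 30)/570 = 15.8% to (90 + 60)/600 = 25%.

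   If 510 per arm gave 80% power for some lipid difference (z = 2.80, two-sided 0.05), the pooled z is 2.80 × (1 − share) × √((510 + r)/510).
   - r = 60: 2.80 × 0.895 × 1.057 = 2.65, power about 75%.
   - r = 90: 2.80 × 0.85 × 1.085 = 2.58, power about 73%.

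   More generally, if a fraction f of values keeps a fraction k of the on-drug difference, the mean difference is multiplied by 1 − f(1 − k). For f from 5% to 15% and k from 0 to 0.5, that runs from 0.85 (f = 15%, k = 0) to 0.975 (f = 5%, k = 0.5).

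The documents give no lipid effect, lipid SD, rescue rate or off-drug retention rate, so none of these results is an estimate for this trial.

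**The case against.** The efficacy default applies only where nothing else is specified, and SAP 6.10.4 names all five lipid parameters and gives them a method. It can be read as the exception. Protocol 10.3.4.5 already uses rank ANOVA with LOCF for safety laboratory measures, and Protocol 10.3.4.6 analyses blood pressure, another 9.1.3 item, under safety. Listing in 9.1.3 therefore does not by itself fix the estimand. SAP 6.1 also lets a change of method be justified in the SAP or in the clinical study report. This much stands: no breach is shown. It remains true that 6.10.4 states neither an estimand nor a reason, and that the SAP revision history does not mention lipids.

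The protocol sentence "The analysis will be conducted for on-treatment without rescue medication data" (10.3.3.4) might be taken to require censored data for lipids. It does not clearly do so. It belongs to the paragraph on longitudinal variables analysed by MMRM; the paragraph on nonlongitudinal variables lacks it.

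One might also stretch the open list in SAP 6.9.3 to cover lipids. The SAP does not say so, and the one section that names them points elsewhere.

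The strongest objection concerns what censoring would deliver. The first scheduled post-baseline lipid sample is at Week 36. A patient who stops drug or is rescued before then has no scheduled on-treatment value for LOCF to carry. An early-termination panel exists, but SAP 6.1 limits inference to scheduled visits unless otherwise stated. The Week 36 censored analysis is thus a comparison of unrescued patients still on drug, who are selected on tolerability and response. That stands, and it is why the all-data analysis should stay.

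**Conclusion.** The mismatch is real and minor. An exploratory efficacy measure has no planned analysis under the default efficacy estimand and no planned baseline-adjusted dose difference, with a confidence interval, in lipid units. This conclusion follows from the wording of the two documents and needs none of the illustrative numbers.

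Two stronger readings are not supported. A reader might infer that the lipid question goes unanswered; it does not, since descriptive changes in lipid units and a test on all data are planned. A reader might also infer that the dose difference is biased toward zero by 10.5% to 15%, with power of 73% to 75%. Those figures assume high retention of off-drug patients, complete loss of effect and equal shares by arm. Even the 90 per arm is uncertain as an off-drug count: Protocol 10.1 and SAP 5.2 speak of completing 36 weeks of treatment, Protocol 5.2 only of completing Week 36. Unequal rescue between arms, or rescue drugs that themselves affect lipids, could move the comparison either way. Size and direction are unknown.

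Lipids lie outside the eight hypotheses in SAP 6.1.4, so no alpha-controlled conclusion is affected.

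**What to change.** Add the lipid parameters to SAP 6.9.3:

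- Use on-treatment-without-rescue data and the linear model already written there: pooled country, treatment and baseline HbA1c stratum as fixed effects, own baseline as covariate. Analyse triglycerides on the log scale and report them as a ratio.
- Report LS mean differences from 1.5 mg with 95% CIs at Week 36. That model stops at Week 36, so for Week 52 either extend it or use the repeated-measures model in SAP 6.11.2 for EQ-5D-5L.
- Keep the all-data rank ANOVA in SAP 6.10.4 as the safety display, and say that it includes post-rescue and off-drug values.
- State that the Week 36 censored analysis covers only unrescued patients still on drug and is to be read beside the all-data analysis.

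The minimum alternative is a sentence saying, with a reason, that lipids are analysed as safety measures only.

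The cost is SAP wording, one more call of an existing model and an extra set of tables. No new data are needed. The price in interpretation is the selected Week 36 set just described.

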10.3.4.5. Laboratory Analyses

Laboratory safety measurements will be summarized. For continuous (numeric) laboratory analytes, the change from baseline by visit will be summarized as detailed in Section 10.3.1. Change from baseline to endpoint (LOCF) will be analyzed using an ANOVA on the ranks with treatment as a fixed effect unless otherwise specified. For subjective (qualitative) laboratory analytes, counts and percentages of patients with normal and abnormal values will be analyzed using Fisher's exact test.

Shift tables of the change from baseline value to the most extreme postbaseline value and from baseline to Week 52 for selected analytes using clinically meaningful thresholds will be summarized.

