The efficacy estimand analysis for a longitudinal continuous variable will employ a mixed-model repeated measure (MMRM) using restricted maximum likelihood to obtain model estimates with Kenward-Roger option to estimate denominator degrees of freedom. The model will include factors for treatment, pooled country, visit, treatment-by-visit interaction, and the baseline as a covariate. The observed margins option will be used in the LSMEANS statement whenever this option is allowed. For analyses of body weight and FSG, the baseline HbA1c strata ($\geq 8.5\%$ [69 mmol/mol] and $< 8.5\%$) will be added in this model as a fixed effect. An unstructured covariance structure will be used to model the within-patient errors. If this model fails to converge, the following covariance structures will be tested in order:

- toeplitz with heterogeneity
- autoregressive with heterogeneity, by visit
- compound symmetry with heterogeneous variances, by visit
- toeplitz
- autoregressive
- compound symmetry without heterogeneous variances, by visit
- compound symmetry

The first covariance structure that converges will be used.

The analysis model for nonlongitudinal continuous variables will be analysis of covariance (ANCOVA) coupled with imputation for missing endpoints unless otherwise noted.

For continuous laboratory measurements for safety, an analysis of variance (ANOVA) on ranks on change from baseline using last observation carried forward (LOCF) at Week 36 (Visit 9) and/or Week 52 (Visit 11) will be used with treatment as a fixed effect.

For all continuous measures, summary statistics will include number of patients, mean, SD, median, minimum, and maximum for both the actual and change from baseline values at each scheduled visit for each treatment unless otherwise specified. Least-squares means (LS means) and standard errors derived from the model will also be displayed for the change from baseline values at each scheduled visit for each treatment. Treatment comparisons will be displayed showing the treatment difference LS means and the 95% CIs between each investigational dulaglutide dose and dulaglutide 1.5 mg (treatment differences) at the same visit, along with the corresponding p-values.

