Summary statistics for categorical measures will include number of subjects and percentages. The proportions of patients achieving target HbA1c $<7.0\%$ and $\leq 6.5\%$ at Week 36 (Visit 9) will be analyzed using a longitudinal logistic regression with repeated measurements. In this model, pooled country, treatment, visit, and treatment-by-visit interaction will be fit as fixed effects, and baseline HbA1c as a covariate. A logistic regression model will be applied for the aforementioned HbA1c target analysis at Week 36 (Visit 9) using LOCF by removing visit-related terms from the corresponding longitudinal logistic regression model.

For the analysis of other categorical measures, Fisher's exact test will be used for treatment comparisons unless otherwise specified. Categorical variables will be summarized by sample size and the number of patients and percentages for each treatment group at each visit. Imputed data may be applied in model-based data analyses, but will not be used in data listings. The latter will only present the non-imputed raw data, including site-reported scheduled and unscheduled visits, or early termination visit data; however, only scheduled visits for the measure of interest will be included in the summary table and statistical inference unless otherwise stated.

All statistical analyses will be conducted with SAS Version 9.4® or higher unless otherwise stated.

For primary DBL, all tables, figures, and listings (TFLs) will use the data up to Week 36 (Visit 9) or the study discontinuation date, whichever is earlier, unless otherwise specified.

For the final DBL delivery, TFLs will use the data up to the end of the treatment period (Week 52 [Visit 11]) or the study discontinuation date, whichever is earlier, unless otherwise stated.

Before each DBL, all key data will be reviewed. Any decision to exclude either subjects or observations from the statistical analyses will be made and documented by the study team, and will include the rationale.

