6.10.1.2.9. Acute Renal Events

Summaries of all treatment-emergent renal safety events will be generated by PT with decreasing frequency by treatment separately for acute renal failure and chronic renal failure. To examine AEs indicating decrease in renal function, the SMQ for Acute Renal Failure and an LSC for chronic renal failure events will be used to search the clinical trial database for events of interest.

A summary and analysis using LOCF will be provided for renal functional laboratory measures: estimated glomerular filtration rate (eGFR) using Chronic Kidney Disease-Epidemiology Collaboration (CKD-EPI); eGFR using CKD-EPI cystatin-C equation (Inker et al. 2012); eGFR using CKD-EPI creatinine-cystatin-C equation (Inker et al. 2012); and creatinine, urine albumin/creatinine ratio (UACR), by treatment. The ANOVA model will be fit with treatment as a fixed effect on the ranked LOCF change from baseline data.

The minimum eGFR (CKD-EPI) value and the maximum creatinine, and UACR will be used for baseline and postbaseline calculations to generate the shift table. The shift table will use eGFR cutoffs (<30 , 30 to <60 , 60 to <90 , and ≥ 90 mL/min/1.73 m²); creatinine cutoffs ($\leq 1 \times$ upper limit of normal [ULN], $>1 \times$ and $\leq 2 \times$ ULN, $>2 \times$ and $\leq 4 \times$ ULN, and $>4 \times$ ULN); and UACR cutoffs (<30 , ≥ 30 , and ≤ 300 , and >300 mg/g).

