A summary report and analysis for treatment-emergent abnormal laboratory values (outside the reference ranges as appropriate) will be provided for each continuous analyte by treatment. Shift tables of the change from baseline value to the maximum postbaseline value to endpoint for selected analytes using clinically meaningful thresholds will be summarized descriptively. A shift table for alanine aminotransferase, aspartate aminotransferase, alkaline phosphatase, total bilirubin level, and direct bilirubin will be generated using the following cutoffs: $\leq 1 \times \text{ULN}$, ($> 1 \times \text{ULN}$ and $< 3 \times \text{ULN}$), ($\geq 3 \times \text{ULN}$ and $< 5 \times \text{ULN}$), ($\geq 5 \times \text{ULN}$ and $< 8 \times \text{ULN}$), and $\geq 8 \times \text{ULN}$.

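### The SAP's laboratory shift tables run to the maximum postbaseline value instead of the protocol's most extreme value, so at the final lock they can miss a fall seen at only one visit

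*SAP*

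**What the plan says.** Protocol 10.3.4.5 (Laboratory Analyses) plans "Shift tables of the change from baseline value to the most extreme postbaseline value and from baseline to Week 52 for selected analytes", with thresholds described as clinically meaningful. This names two targets: the extreme postbaseline value, with no direction fixed, and the Week 52 value.

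SAP 6.10.4 (Clinical Laboratory Evaluation) has instead "Shift tables of the change from baseline value to the maximum postbaseline value to endpoint for selected analytes", also with clinically meaningful thresholds. Neither sentence lists the selected analytes or their thresholds.

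Other SAP text that bears on the point:

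- The sentence just before the shift-table sentence in 6.10.4 promises a summary and analysis of "treatment-emergent abnormal laboratory values (outside the reference ranges as appropriate) will be provided for each continuous analyte by treatment".
- SAP 6.1 says of continuous outcomes that "summary statistics will include number of patients, mean, SD, median, minimum, and maximum for both the actual and change from baseline values", by visit and by arm. It also plans a rank ANOVA on the change in continuous safety laboratory measures, with the last observation carried forward.
- SAP 6.10.1.2.9 sets a direction for the renal tables: "The minimum eGFR (CKD-EPI) value and the maximum creatinine, and UACR will be used for baseline and postbaseline calculations".
- SAP 6.1 says that "only scheduled visits for the measure of interest will be included in the summary table and statistical inference unless otherwise stated", and that outputs for the primary lock "will use the data up to Week 36 (Visit 9) or the study discontinuation date, whichever is earlier". Final-lock outputs run to Week 52.

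**The concern.** Most extreme can mean the lowest or the highest value, whichever matters for the analyte. Maximum means only the highest. For liver tests or pancreatic enzymes the two coincide. For an analyte where a fall is the harm, a table of the maximum classifies each patient by the most reassuring value on record.

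The SAP recognizes direction elsewhere: it takes the minimum for eGFR, and Table GBGL.4 sets low as well as high limits for blood pressure. The general sentence in 6.10.4 has no such rule, although Protocol Appendix 2 shows that sodium, potassium, calcium, albumin, hemoglobin, leukocytes, neutrophils and platelets are all measured.

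The phrase running from the maximum value to endpoint can also be read in more than one way: a shift to the maximum, a shift to the endpoint value, or both. A programmer cannot tell whether the protocol's Week 52 shift is still wanted.

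What is at stake is the readability of low-side laboratory changes by dose. The trial exists to compare doses, so a graded table that shows movement in one direction only is an avoidable gap.

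**Working it through.** The plan states no figure on this point, so there is none to reproduce. The check compares the two rules at each database lock and then illustrates the possible size of the loss.

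**1. Scheduled draws (Protocol Section 2, Schedule of Activities).** Hematology is drawn at Visit 1, Visit 9 (Week 36), Visit 11 (Week 52) and early termination. The chemistry panel has the same visits plus Visit 801. By default SAP 6.1 keeps scheduled visits only and ends the final-lock data at Week 52.

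- Primary lock: one scheduled postbaseline value, so maximum = minimum = the Week 36 value. The two rules agree.
- Final lock: two scheduled postbaseline values, Weeks 36 and 52. The rules can differ.

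If unscheduled or early-termination values were also admitted, the rules could differ at the primary lock too.

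**2. What the table shows at the final lock for a low-side analyte.**

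- Low at both visits: the maximum is low, so the patient shows as low, provided the threshold grid has a low category.
- Low at one visit only: the maximum is the other, non-low value, so the patient does not show as low.
- The minimum shows both kinds of patient.

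**3. Illustration.** The documents give neither the proportion of low values nor the between-visit correlation, so both are assumed. Let p be the proportion low at each visit and ρ the correlation of two bivariate normal values, with c = Φ⁻¹(p).

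- Shown by the maximum: P(both low) = Φ₂(c, c; ρ)
- Shown by the minimum: P(either low) = 2p − P(both low)
- Share shown by the maximum = P(both low) / P(either low)

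| p | ρ | Both low (maximum) | Either low (minimum) | Share shown |
|---|---|---|---|---|
| 2% | 0.3 | 0.17% | 3.83% | 4% |
| 2% | 0.5 | 0.34% | 3.66% | 9% |
| 2% | 0.8 | 0.85% | 3.15% | 27% |
| 5% | 0.3 | 0.71% | 9.29% | 8% |
| 5% | 0.5 | 1.22% | 8.78% | 14% |
| 5% | 0.8 | 2.48% | 7.52% | 33% |
| 10% | 0.3 | 2.16% | 17.84% | 12% |
| 10% | 0.5 | 3.24% | 16.76% | 19% |
| 10% | 0.8 | 5.62% | 14.38% | 39% |

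For the middle row, 2 × 5% − 1.22% = 8.78%, and 1.22 / 8.78 = 14%. Over the whole grid the maximum shows 4% to 39% of patients who are low at either visit.

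**4. What the other outputs recover.** The abnormal-value summary covers each continuous analyte by treatment, and a value below the lower limit is outside the reference range. It does not say that low and high are reported separately, and it gives no graded thresholds and no movement from a baseline category. The by-visit minimum is one value per arm, not a count of patients. The rank ANOVA responds to general falls as well as rises, but at the final lock it uses the Week 52 endpoint. It would miss a fall at Week 36 that had recovered, and a few large falls hardly move it.

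**The case against.** The best defense is that these are descriptive tables for unnamed analytes, and that the SAP reports low values elsewhere. Where the SAP does name analytes for a shift table, the direction suits them: the maximum for pancreatic enzymes, creatinine and UACR, multiples of the upper limit for liver tests, and the minimum for eGFR. Sodium, potassium, hemoglobin and platelets are named for a shift table in neither document. That stands, and it keeps the point small. It does not justify a general rule that points the wrong way for any low-side analyte that may be selected.

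Several stronger readings are tempting, and the documents do not support them.

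- A reader might infer that harmful falls cannot appear by dose at all. They can, through the abnormal-value summary and the by-visit minima. A patient with low potassium at Week 36 and a normal value at Week 52 can be counted in that summary, and the shift table at the Week 36 lock would not hide the low value.
- A reader might infer that the Week 52 shift was deleted. SAP 6.10.4 defines endpoint as Week 36 for the primary lock and Week 52 for the final lock. One missing word could explain the sentence, so the text is ambiguous but a deletion is not shown.
- A reader might infer that the SAP breaks its own rule on justifying changes. SAP 6.1 allows the justification to appear in the SAP or the clinical study report, so silence in the SAP is not a breach. It does contrast with SAP 6.1.2.1 and 6.9.2.2, which explain other departures from the protocol.
- A reader might assume independent draws. At 2% low per visit that gives 0.04% low at both against 3.96% at either, so about 99% hidden. Independence within one patient is implausible, and the 2% is itself assumed.
- A reader might infer that falls in electrolytes or blood counts are expected dose-related harms. The documents call nausea, vomiting and diarrhea common (Protocol 10.3.4.4, SAP 6.10.1.3), but they do not identify such falls as dose-related harms or list them among the events of special interest.

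**Conclusion.** This is a real but minor inconsistency. The SAP narrows the protocol's shift rule from the most extreme to the maximum postbaseline value, without explanation and in a sentence that does not parse cleanly.

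The consequence is confined to graded low-side shifts at the final lock, for whichever selected analytes have a harmful low side. On scheduled data nothing is lost at the Week 36 lock, and no efficacy result or error rate is affected. The 4% to 39% range shows how a maximum-only table would behave under assumed low rates and correlations. It does not estimate what this trial would miss, and it applies only if the selected analytes include low-side ones with a low threshold category.

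**What to change.** In SAP 6.10.4, restore the protocol's two-part rule:

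- shift from baseline to the most extreme postbaseline value in the direction of concern: the minimum where a fall is the harm, the maximum where a rise is, and both where both matter;
- shift from baseline to Week 52 at the final lock.

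List the selected analytes with the direction and thresholds for each, and state in the same section that treatment-emergent low and high values are reported separately. If the restriction to the maximum was intended, give the reason in the SAP or the clinical study report.

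The cost is a few sentences in the SAP and a few more descriptive tables. All the data are already collected under the Schedule of Activities.
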